We initially focus on the cohort that is in the range 2500-5000 IEQ/kg, since these participants will be the largest fraction of enrollees. It is anticipated that the percentage of such patients achieving insulin independence will be increased from 23% in the placebo control arm to 55% in the reparixin arm. Using standard statistical formulas based on the approximation of the binomial distribution by the normal distribution, the sample size of 44 patients per arm provides 90% power to detect a 23% vs. 55% true difference when using a Pearson Chi-Square Statistic having the traditional (one-sided) 2.5% false positive error rate. Even accounting for the discreteness, the power should be in the 87%-90% range. Furthermore, with 44 patients per arm, statistical significance (i.e., one-sided p=0.025) will be obtained if the estimated difference is 22.7% (10/44) vs. 43.2% (19/44), which is an estimated 20.5% increase in patients achieving insulin independence. Hence, with 44 patients per arm, statistical significance is achieved with an estimated effect size that is clinically meaningful.

Even though the largest percentage of patients will be in the cohort receiving IEQ/kg in the range 2500-5000 IEQ/kg, the trial will also enroll participants in two additional strata: <2500 IEQ/kg and >5000 IEQ/kg. As noted above, we are presuming the middle strata would have an increase from 23% to 55% in percentage of patients achieving insulin independence. This is an odds ratio higher than 4. If we have an odds ratio of approximately 4.3 to 4.5 in the other 2 strata and if approximately ½ of the patients would be from the 2500-5000 IEQ/kg stratum, then only a modest increase of about 12 additional patients beyond the 88 patient sample size would be needed to maintain the statistical power of the trial. An increase in success rate from 13% to 40% in the <2500 IEQ/kg stratum would be an odd ratio of 4.4 and an increase in success rate from 55% to 84% in the >5000 IEQ/kg stratum would be an odd ratio of 4.3.

Based on these considerations, it is planned to enroll 100 patients in this trial who receive IAT, with the expectation that there will be approximately 5 others who do not receive IAT. Under such a plan, the trial would not be overpowered even if all participants were in the 2500-5000 IEQ/kg stratum since statistical significance (i.e., one-sided p=0.025) would be obtained with 52 patients per arm if the

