## 9.2. RANDOMIZATION

Patient will be randomized in a 1:1 fashion to either reparixin or placebo.

The randomization list will be generated with a computer procedure by the method of random permuted blocks in which treatment (in blocks of 4) will be balanced within centres. A master randomization list will be generated, randomizing an excess of patients (a maximum of 40 for each site – additional 8 patients for the site of the Primary Investigator) to allow competitive recruitment within each centre.

The randomization list will be prepared by an independent statistician and provided to Dompé in a sealed envelope to prevent unblinding.

Similarly, individual treatment codes will be provided as a tamper-resistant system (either a sealed envelope or a scratch card). Such system will definitely allow to recognize if the code has been broken and guarantees detection of any code misuse. Individual treatment codes will be provided to:

- the Pharmacist (or designee) within each participating site for Investigational Product preparation;
- the Dompé Pharmacovigilance department for safety procedures.

The Investigators can request to an independent facility (either by telephone or web based system) an individual code in the event of an emergency only, where knowledge of the blinded treatment for that patient could influence further patient care. Any potential unauthorized code break and the reason behind it will be recorded.

The randomization codes will also be accessible to an Independent Statistician (liaison between the CRO database and DMC Biostatistician) who will generate the reports for the Data Monitoring Committee (DMC) evaluation (see Section 12.5).

The randomization code will be broken at study completion, i.e. when the last patient has completed his/her last follow-up visit (planned 365 days after islet infusion), and once the database has been locked.

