Initial focus is placed on the cohort that is in the range 2500-5000 IEQ/kg, since these participants will be the largest fraction of enrollees. It is anticipated that the percentage of such patients achieving insulin independence will be increased from 23% in the placebo control arm to 55% in the reparixin arm. Using standard statistical formulas based on the approximation of the binomial distribution by the normal distribution, the sample size of 44 patients per arm provides 90% power to detect a 23% versus 55% true difference when using a Pearson Chi-square statistic having the traditional (one-sided) 2.5% false positive error rate. Even accounting for the discreteness, the power should be in the 87% to 90% range. Furthermore, with 44 patients per arm, statistical significance (i.e., one-sided  $p=0.025$ ) will be obtained if the estimated difference is 22.7% (10/44) versus 43.2% (19/44), which is an estimated 20.5% increase in percentage of patients achieving insulin independence. Hence, with 44 patients per arm, statistical significance is achieved with an estimated effect size that is clinically meaningful.

Even though the largest percentage of patients will be in the cohort receiving IEQ/kg in the range 2500-5000 IEQ/kg, the trial will also enroll participants in two additional strata: <2500 IEQ/kg and >5000 IEQ/kg. As noted above, we are presuming the middle strata would have an increase from 23% to 55% in percentage of patients achieving insulin independence. This is an odds ratio higher than 4. If we have an odds ratio of approximately 4.3 to 4.5 in the other 2 strata and if approximately 1/2 of the patients would be from the 2500-5000 IEQ/kg stratum, then only a modest increase of about 12 additional patients beyond the 88 patient sample size would be needed to maintain the statistical power of the trial. An increase in success rate from 13% to

REP0112

Statistical Analysis Plan

40% in the <2500 IEQ/kg stratum would be an odds ratio of 4.4 and an increase in success rate from 55% to 84% in the >5000 IEQ/kg stratum would be an odds ratio of 4.3.

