### 3.4 Randomization

Patients will be randomized in a 1:1 fashion to either reparixin or placebo.

The randomization list will be generated with a computer procedure by the method of random permuted blocks in which treatment (in blocks of 4) will be balanced within centres. A master randomization list will be generated, randomizing an excess of patients (a maximum of 40 for each site) to allow competitive recruitment within each centre.

The randomization list will be prepared by an independent statistician and provided to Dompé in a sealed envelope to prevent unblinding.

Similarly, individual treatment codes will be provided via a tamper-resistant system (either a sealed envelope or a scratch card). Such a system will definitely allow recognition of whether the code has been broken and guarantees detection of any code misuse. Individual treatment codes will be provided to:

- the Pharmacist (or designee) within each participating site for investigational product preparation;
- the Dompé Pharmacovigilance Department for safety procedures.

The investigators can request to an independent facility (either by telephone or web based system) an individual code in the event of an emergency only, where knowledge of the blinded treatment for that patient could influence further patient care. Any potential unauthorized code break and the reason behind it will be recorded.

The randomization codes will also be accessible to an independent statistician (liaison between the contract research organization [CRO] database and Data Monitoring Committee [DMC] biostatistician) who will generate the reports for the DMC evaluation.

The randomization code will be broken at study completion, i.e. when the last patient has completed his/her last follow-up visit (planned at 365 days after islet infusion), and once the database has been locked.

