#### Primary Analysis

The proportion of insulin-independent patients will be compared between treatment groups using the Cochran-Mantel-Haenszel test stratified by baseline IEQ/kg (<2500 IEQ/kg, 2500-5000 IEQ/kg, and >5000 IEQ/kg). The hypothesis to be tested is:

Null Hypothesis,  $H_0$ :  $p_{\text{reparixin}} \leq p_{\text{placebo}}$  for all baseline IEQ/kg strata

Alternative Hypothesis,  $H_A$ :  $p_{\text{reparixin}} > p_{\text{placebo}}$  for at least one baseline IEQ/kg strata

The significance level used for statistical testing will be 2.5% and a one-sided test will be used. The 95% confidence interval for treatment proportions and the one-sided 95% confidence interval for the difference in treatment proportion between reparixin and placebo will be produced.

As a sensitivity analysis, the primary analysis will be repeated for the ITT population, dropping from the analysis any site with >20% of subjects not having data for the primary endpoint recorded; subjects will be considered to not have data recorded for the primary endpoint if they have discontinued the study prior to attending the Day 365 visit or if they have attended the Day 365 visit but did not have the primary endpoint recorded. The intent is to examine the sensitivity of the primary analysis to sites lacking a reasonable number of patients with data captured for the primary endpoint.

The relevance of the treatment-by-site interaction will be investigated using a logistic regression model which will include the main effect of treatment and IEQ/kg infused at IAT (<2500 IEQ/kg,

REP0112

Statistical Analysis Plan

2500-5000 IEQ/kg, and >5000 IEQ/kg) and site as covariates. The analysis variable for treatment will be coded such that the reference treatment is placebo, the analysis variables for IEQ/kg infused at IAT will be coded such that the reference group is <2500 IEQ/kg, and the analysis variables for site will be coded such that the reference site is Site 1. The treatment-by-site interaction will be examined, and if not significant at the 0.10  $\alpha$ -level, will be removed from the model. The hypothesis to be examined is:

Null Hypothesis,  $H_0$ :  $\beta_{\text{treatment}} \leq 0$

Alternative Hypothesis,  $H_A$ :  $\beta_{\text{treatment}} > 0$

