The treatment effect ( $\beta_{\text{treatment}}$ ) will be declared significantly greater than 0 at the 0.025  $\alpha$ -level. A model parameter estimate and the corresponding standard error, p-value, and odds ratio with a one-sided 95% confidence interval will be presented for the treatment effect.

The logistic regression sensitivity analysis will also be performed for the ITT population, dropping from the analysis any site with >20% of subjects not having the primary endpoint recorded, using the same approach used for the sensitivity analysis of the primary endpoint.

As further sensitivity analysis, the primary endpoint analysis and the corresponding logistic regression analysis will be repeated including Site 01 only, which is the largest site with the greatest number of patients receiving IAT, having possibly the best treatment balance, having a high rate of primary endpoint data capture, and also being the site with the highest experience in the field and thus transplanting patients under highly reproducible surgical and clinical conditions. When performing the logistic regression analysis, site will no longer be considered a covariate in the model. The intent of these analyses is to examine the sensitivity of the primary analysis to the low enrollment/treatment balance, lesser experience level, and lower rates of retention which may be present at the other sites.

For both the primary and sensitivity analyses, patients who die or who discontinue before the primary endpoint assessment at Day 365  $\pm$  14 days after IAT, or those who reach the Day 365 visit but have no primary endpoint assessment, will be treated as primary endpoint failures.

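### The primary CMH test leaves out centre, the only randomization factor: no validity problem, but about 2 to 4 points of power are lost if Site 01 and the other sites differ strongly

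*SAP*

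**What the plan says.** Protocol 9.2 specifies "random permuted blocks in which treatment (in blocks of 4) will be balanced within centres", and SAP 3.4 repeats this. Allocation is 1:1. Centre is the only stratification factor. IEQ/kg cannot be one, because it is known only after islet isolation, once the infusion has started.

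The primary comparison in SAP 7.5.1 is "compared between treatment groups using the Cochran-Mantel-Haenszel test stratified by baseline IEQ/kg", in three groups (<2500, 2500-5000, >5000). On level, it states: "The significance level used for statistical testing will be 2.5% and a one-sided test will be used". The Protocol synopsis and 9.4.2 also name only the three IEQ/kg groups. None of these places explains why centre is left out.

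Site does appear elsewhere. SAP 7.5.1 plans, as supporting work:
- a logistic regression with treatment, IEQ/kg group and site;
- a treatment-by-site check at the 0.10 level;
- repeats that drop sites with more than 20% of primary endpoints missing;
- a repeat in Site 01 alone, intended to examine sensitivity to low enrolment or treatment balance, "lesser experience level, and lower rates of retention which may be present at the other sites".

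Missing primary outcomes count as failures throughout. The secondary mixed models (SAP 7.5.2.1 to 7.5.2.3) include site.

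**The concern.** Blocking within centre forces the arms to be nearly equal in size at each site. Differences in success rate between sites then add almost nothing to the true variability of the treatment comparison. A test that does not know about sites still counts those differences as noise. Its standard error is too large, its true level falls below 2.5%, and it gives up some power.

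The trial has one dominant site. Protocol 3.1 allows up to 48 patients at the Primary Investigator's site, and the SAP singles out Site 01 as the largest and most experienced. If success differs strongly between that site and the rest, a real benefit is somewhat more likely to miss the 2.5% threshold than it need be. A site-adjusted sensitivity analysis cannot rescue a missed primary test.

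**Working it through.** **The plan's own figure.** SAP 3.3 states that "the sample size of 44 patients per arm provides 90% power to detect a 23% versus 55% true difference" at one-sided 2.5%. With unpooled variance,

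n = (1.960 + 1.282)² × (0.23×0.77 + 0.55×0.45) / (0.55 − 0.23)² = 10.51 × 0.4246 / 0.1024 = 43.6, so 44 per arm.

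Power at 44 per arm is 90.3% by this formula, 88.2% with pooled variance and 88.8% by exact binomial calculation. The stated 90%, and 87-90% allowing for discreteness, are reproduced.

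**Inputs from the documents.**
- Success rates, placebo vs reparixin: 13% vs 40%, 23% vs 55%, 55% vs 84% (Protocol 9.1, e.g. "An increase in success rate from 13% to 40% in the <2500 IEQ/kg stratum would be an odd ratio of 4.4").
- Stratum mix 34/42/24% (SAP 3.3).
- Nine sites (Protocol amendment, reason for change to 3.1).
- Up to 48 patients at the largest site (Protocol 3.1).
- Blocks of 4 within centre, 1:1; missing counted as failure.

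**Assumptions not in the documents.**
- N = 104 (52 per arm, as in SAP 3.3).
- The Primary Investigator's site is Site 01, with 48 patients; eight other sites have 7 each (48 + 8×7 = 104).
- 3% of outcomes missing at Site 01 and 20% elsewhere.
- A Site 01 advantage (gap) of 0 to 2 logits, half added at Site 01 and half subtracted elsewhere.

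**Test statistic.** In stratum k, let a be reparixin successes, d all successes, n₁ and n₀ the arm sizes, and n their sum. Then

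z = Σ(a − n₁d/n) / √Σ[n₁n₀d(n − d) / (n²(n − 1))],

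and the test rejects if z > 1.96. The planned test sums over 3 IEQ/kg strata. The alternative sums over 6: IEQ/kg group × (Site 01 vs others).

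**Results**, 20,000 simulated trials per setting. Monte Carlo standard error is about √(0.8×0.2/20,000) = 0.3 points for each power and √(0.025×0.975/20,000) = 0.001 for each alpha.

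| Gap (logits) | Site odds ratio | Power, planned | Power, six strata | Alpha, planned | Alpha, six strata |
|---|---|---|---|---|---|
| 0 (retention only) | 1.0 | 82.8% | 82.3% | 0.026 | 0.025 |
| 0.7 | 2.0 | 81.6% | 82.2% | 0.024 | 0.026 |
| 1.2 | 3.3 | 79.4% | 81.7% | 0.022 | 0.025 |
| 1.6 | 5.0 | 75.9% | 79.9% | 0.019 | 0.024 |
| 2.0 | 7.4 | 71.2% | 78.2% | 0.016 | 0.024 |

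A second run of the same size gave 82.2 vs 81.6% with retention differences only, 79.2 vs 81.3% at 1.2 and 75.9 vs 80.3% at 1.6. Planned alpha was 0.021 at 1.2 and 0.018 at 1.6. With no gap and no missing data, power was 91.3 vs 90.6%, a cost of 0.7 points.

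**Why retention alone does nothing.** For a placebo patient in the middle stratum, 3% vs 20% missing gives observed success of 0.23×0.97 = 22.3% vs 0.23×0.80 = 18.4%, a gap of 3.9 points. Adding 1.2 logits (logit of 0.23 is −1.208; ±0.6 gives 35.2% and 14.1%) makes it 0.352×0.97 = 34.2% vs 0.141×0.80 = 11.3%, a gap of 22.9 points. Only a gap of that order affects the test noticeably.

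**Stratifying by all nine sites.** With IEQ/kg × nine sites (27 cells), no missing data and site effects of SD 0, 0.5, 1.0 and 1.5 logits, power was 84, 84, 80 and 73%, against 91, 89, 83 and 73% for the planned test. That costs 3 to 7 points unless sites differ very strongly. The six-cell version avoids sparse cells: its smallest expected cell is 0.24×48 = 11.5 patients.

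**The case against.** The strongest reply is that the loss depends on a site effect the documents do not supply. A reader might infer that the SAP expects sites to differ, but it says only that lesser experience and lower retention may be present elsewhere, when giving the purpose of a sensitivity analysis. It predicts no difference in success rates. A reader might also infer that counting missing outcomes as failures makes site prognostic enough to matter. It does not: in the retention-only case the planned test was not conservative and was marginally the better of the two. The gaps that matter are site odds ratios of about 3 to 5 within the same IEQ/kg group. The upper end exceeds the drug effect assumed in the sample size (odds ratios 4.1 to 4.5). All of this stands, and it limits the size of the point.

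It also stands that a site-adjusted logistic model is already planned, and that Site 01 versus the rest is only a coarse version of the randomization factor. Most of the gain is recovered alpha: once both tests are held to the same true level, they differ by about a point or less. But the trial will be judged at the fixed 2.5% cut-off, so the recovered alpha has practical value. The logistic model is a supporting analysis, and a large-sample score test with all nine sites ran liberal in simulation (0.028 to 0.034), so it is not an obvious replacement for the primary test.

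**Conclusion.** The design and the deciding test do not match: centre is a randomization factor and is absent from the primary analysis without explanation. The consequence is modest and conditional. At an assumed Site 01 advantage of 1.2 to 1.6 logits, the planned test runs at a one-sided level of about 0.021 to 0.018 and loses about 2 to 4 points of power. At 0.7 logits or below, or with retention differences only, the two tests differ by about half a point in either direction.

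A reader might conclude that the planned test is invalid. The documents and the calculations do not support that: its error is on the conservative side and type I error is not inflated. This is a cheap improvement in efficiency and consistency. The figures rest on assumed site gaps, missing-data rates and site sizes, and on Site 01 being the 48-patient site.

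**What to change.** Before database lock, and without unblinded data, change SAP 7.5.1 so that the primary CMH test is stratified by IEQ/kg group × (Site 01 vs all other sites pooled), six strata. Use the same strata for the confidence interval for the difference in proportions. Site 01 is already named in the SAP, so the factor needs no outcome data to define.

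Record the change and its reason in SAP 1.2, which now lists no changes from protocol, because Protocol 9.4.2 (and the synopsis) specify the three IEQ/kg groups alone. Keep the logistic model with its full site term, and leave the other site sensitivity analyses as they are. Do not stratify the CMH by all nine sites.

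Cost: a short edit, a recorded departure from the protocol, and about 0.5 to 0.7 points of power if sites turn out not to differ. If the sponsor prefers the three-stratum test, the SAP should say why centre is left out.

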## 9.3. ANALYSIS POPULATION

The Intent to Treat (ITT) population will consist of all patients who are randomized and receive the Investigational Product (either reparixin or placebo); it will be based on the treatment randomized, regardless of the treatment actually received. Patients will be in the ITT analysis whether or not they receive IAT, because exclusions cannot be made for events occurring after randomization that could be influenced by the randomized assignment. The primary and secondary efficacy analyses will be presented primarily for the ITT Population.

The Safety population will consist of all randomized patients and will be based on the treatment actually received. The Safety population will be used to present the demographic and baseline data, and all safety data.

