#### **9.4.6. Missing data**

All reasonable efforts will be made to reduce the rate of missing data, since any method used for imputation for missing observations would be based on untestable assumptions that likely would be invalid.

Investigators will be trained about the importance of patient retention and full data capture. Also, any reasonable attempts should be made by the Investigators to emphasize continued patient's participation for the full duration of the trial (see details in Section 7.3.1 and 10.2). However, in order to minimize missing data, if a patient cannot refer to the site for a planned follow-up visit, the Investigator will try to obtain any relevant information from the patients, including documents/laboratory results available from local medical care.

Subjects who die before the primary endpoint assessment at 12 months will be treated as failures in the efficacy analysis. Additionally, for the primary analysis, patients who are lost to follow-up by 12

---

months will be considered as failures, with the recognition that the procedures described in this section have been developed to ensure the number of patients who are lost to follow-up will be very small.

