## 5 DEFINITIONS AND DERIVED VARIABLES

Study Day Relative to Date of First Date of Investigational Product Administration: Day 1 will be defined as the first date on which infusion of investigational product is started. Positive study days will be counted forward from Day 1. Day -1 will be the date immediately preceding Day 1, and negative study days will be counted backward from Day -1.

Study Day Relative to Date of Islet Auto-Transplantation: Day 0 will be defined as the date on which islet are infused. Positive study days will be counted forward from Day 0. Day -1 will be the date immediately preceding Day 0, and negative study days will be counted backward from Day -1.

Visit Windows: For the per protocol population (see Section 6 of this SAP), data recorded at the Day 75 and Day 365 visits will be included in summarization and analysis only if the Day 75 and Day 365 visits fall within 14 days of the target study day relative to the date of IAT as indicated in the following table.

Visit	Target Study Day Relative to Date of IAT	Acceptable Range of Study Days Relative to IAT
Day 75	75	61 to 89
Day 365	365	351 to 379

Area Under the Curve (AUC) Normalized by the Number of IEQ/kg, C-peptide: When C-peptide values are below the limit of detection (0.05 ng/mL), a value of 0.05 ng/mL will be assumed in the calculation of area under the curve. Missing C-peptide values will be imputed via linear interpolation, and the average of the two basal samples (values, and mid-point of sample times) will be used as the first sample in the computation of the AUC. Once these rules have been applied to the data, AUC for C-peptide will be computed using the trapezoidal rule, and normalized by dividing the computed AUC value by the total IEQ/kg infused during IAT as recorded on Page 12 of the CRF. For ease of interpretation, the AUC value obtained will be divided by the total time the scale is assessed for reporting purposes. Computation of AUC will be based on actual collection times, unless actual collection time is missing, in which case the scheduled collection time will be used.

REP0112

Statistical Analysis Plan

Other definitions and derived variables are found within the applicable subsections of Section 7, Statistical Methods.

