## 6 ANALYSIS POPULATIONS

Five analysis populations will be identified and used in the summarization and analysis of data, namely all screened patients, all randomized patients, intent to treat, per protocol, and safety.

- All Screened Patients: This population will include all patients screened for participation in the trial.
- All Randomized Patients: This population will include all patients randomized to investigational product in the trial.
- Intent to Treat: This population will consist of all patients who are randomized and receive the investigational product (either reparixin or placebo). Summarization and analysis of this population will be based on randomized treatment, regardless of treatment actually received. Eligible patients will be included in this population whether or not they receive IAT, because exclusions cannot be made for events occurring after randomization that could be influenced by the randomized assignment.
- Per Protocol: This population will consist of all patients in the ITT population who meet all of the following criteria:
  - Received IAT
  - Completed 7 days of investigational product dosing
  - No major protocol violations, including violations of inclusion/exclusion criteria, errors in treatment assignment, use of prohibited medication, etc.
  - Visits occurring on Day 75 ± 14 days from IAT and Day 365 ± 14 days from IAT
  - Insulin-independence status recorded at Day 365 ± 14 days from IAT

Further criteria for exclusion from the PP population may be identified during the data review meeting held prior to database lock.

- Safety: This population will consist of all randomized patients. Summarization and analysis of this population will be based on treatment actually received.

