### 7.5.1 Primary Variable

The primary variable is the proportion of insulin-independent patients at Day 365 ± 14 days after IAT. The number and percentage of patients who are insulin-independent at Day 365 ± 14 days after IAT will be presented by treatment group overall and by IEQ/kg (<2500 IEQ/kg, 2500-5000 IEQ/kg, and >5000 IEQ/kg) infused at IAT.

The percentage of patients who are insulin-independent at Day 365 ± 14 days after IAT will also be presented graphically as a bar chart overall and by IEQ/kg group. Overall and within each IEQ/kg group there will be bars for reparixin and placebo.

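### Does the primary test leave dosed patients who never receive an islet transplant without an IEQ/kg stratum?

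*SAP*

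**What the plan says.** On who is analysed, the two documents agree. SAP section 6 states "Eligible patients will be included in this population whether or not they receive IAT, because exclusions cannot be made for events occurring after randomization", and Protocol 9.3 states "Patients will be in the ITT analysis whether or not they receive IAT". Dosing is the condition for entry: a randomized patient who never starts the infusion is outside ITT.

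On stratification, SAP 7.5.1 specifies a "Cochran-Mantel-Haenszel test stratified by baseline IEQ/kg" with classes <2500, 2500-5000 and >5000. The descriptive summary in the same section uses the amount infused ("2500-5000 IEQ/kg, and >5000 IEQ/kg) infused at IAT"), and so does the logistic model ("main effect of treatment and IEQ/kg infused at IAT"). SAP section 5 names a data source for IEQ/kg only where it defines the C-peptide AUC, which is divided by the "total IEQ/kg infused during IAT as recorded on Page 12 of the CRF".

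On outcome, SAP 7.5.1 counts as failures "patients who die or who discontinue before the primary endpoint assessment", together with those who attend Day 365 without an endpoint assessment. Protocol 9.4.6 says "Subjects who die before the primary endpoint assessment at 12 months will be treated as failures in the efficacy analysis" and adds losses to follow-up. Neither rule names patients without a transplant. Section 3.2.1 of the SAP addendum, on the primary variable, was not available for this check and may address them.

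**The concern.** A patient can be dosed, have no islets infused, and still belong to ITT. If the IEQ/kg field is empty for that patient, standard software drops the record from both the stratified test and the logistic model. That would be a post-randomization exclusion of the kind SAP section 6 rules out.

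The outcome also looks unsettled. Under Protocol 6.3.2, having no transplant stops the investigational product but does not withdraw the patient from the study. SAP 7.2 allows follow-up to end only for death or withdrawal of consent. Exclusion criterion 9 means these patients entered without diabetes, and Day 365 is counted from a transplant that did not happen. A patient in this position who stays off insulin could conceivably be scored as a success.

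At stake is whether two unwritten coding choices, stratum and outcome, could decide a confirmatory p-value labelled ITT.

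**Working it through.** **The plan's own figure.** Protocol 9.1 and SAP 3.3 give 90% power for 23% vs 55% with 44 per arm at one-sided 0.025. The unpooled normal approximation gives 0.32 / √[(0.23×0.77 + 0.55×0.45)/44] = 0.32/0.0982 = 3.26. Then 3.26 − 1.96 = 1.30, and Φ(1.30) = 90.3%. Exact enumeration of the Pearson test gives 88.8%, inside the stated 87% to 90%. The figure reproduces.

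**How many patients.** The plan expects about 5 untransplanted in addition to 100 transplanted. At the amendment, 89 − 86 = 3 randomized patients had not been transplanted. Neither count is limited to dosed patients. Infusion starts only 6 to 18 hours before the islets, so patients lost before that window are outside ITT. Five is used below as an upper value.

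**Stratum choice.**
- Inputs: 50 transplanted patients per arm, spread as in the recent series (34/42/24%), which gives 17, 21 and 12.
- Success rates from the sample-size section: 40/55/84% on reparixin and 13/23/55% on placebo. The null case uses the placebo rates in both arms.
- Test: z = Σ(a − E)/√ΣV, with E = n₁m/N and V = n₁n₀m(N − m)/[N²(N − 1)] in each stratum, no continuity correction, rejecting at z ≥ 1.96.
- All outcomes were enumerated exactly. Five untransplanted patients were either omitted or placed in <2500 as failures.

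With the five omitted, power is 90.2% and the false-positive rate 2.5%. With them placed in <2500:

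| Split, reparixin:placebo | Weight | Power | Decision differs (design rates) | False-positive rate |
|---|---|---|---|---|
| 0:5 | 1/32 | 93.60% | 3.43% | 3.47% |
| 1:4 | 5/32 | 92.48% | 2.30% | 2.97% |
| 2:3 | 10/32 | 90.86% | 0.69% | 2.60% |
| 3:2 | 10/32 | 89.16% | 1.01% | 2.30% |
| 4:1 | 5/32 | 87.21% | 2.96% | 2.04% |
| 5:0 | 1/32 | 85.02% | 5.15% | 1.79% |

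The weights are Binomial(5, 0.5), from 1:1 randomization. Averages:
- Power: (93.60 + 5×92.48 + 10×90.86 + 10×89.16 + 5×87.21 + 85.02)/32 = 89.9%.
- Decision differs: (3.43 + 5×2.30 + 10×0.69 + 10×1.01 + 5×2.96 + 5.15)/32 = 1.6%.
- False-positive rate: (3.47 + 5×2.97 + 10×2.60 + 10×2.30 + 5×2.04 + 1.79)/32 = 2.5%.

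With 3 such patients, average power is 90.0% and the decision differs in 1.4% of trials. With 1 patient it differs in 1.0%, and with none in 0%. A separate stratum holding only failures has E = 0 and V = 0, so it gives the same result as omission.

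**A case built to sit at the boundary.** Take successes of 3/17, 12/21 and 8/12 against 2/17, 5/21 and 7/12.
- Omitted: z = (23 − 18.5)/√5.157 = 1.982, p = 0.0238.
- Five failures split 3:2 in <2500: z = (23 − 18.564)/√5.177 = 1.950, p = 0.0256.

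The choice can therefore matter, but only for a result already at the threshold.

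**Outcome, case by case.**
1. Dies, discontinues, or is lost to follow-up: a failure under SAP 7.5.1 or Protocol 9.4.6.
2. Attends Day 365 without an endpoint assessment: a failure under SAP 7.5.1.
3. Pancreas fully removed, no islets given: Protocol 2.5 describes the absence of endogenous insulin after total pancreatectomy. Such a patient would need insulin and fails on assessment.
4. Surgery abandoned with pancreas left in place, still followed and off insulin: the only open case. The endpoint is defined following IAT and timed from it, so the patient cannot meet it as written.

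**The case for a change.** The strongest reply is that a blank is not a zero. A confirmatory analysis should not depend on what a programmer assumes, and a rule chosen after the data are seen is worse than one written beforehand. The near-boundary example gives this force. At the 3:2 split in <2500, scoring one reparixin patient as a success moves p from 0.0256 to 0.0167, and scoring one placebo patient as a success moves it to 0.0451. Fisher's test of untransplanted rates in SAP 7.4.1 and the overall proportions report these patients but do not put them into the primary test.

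It stands that no sentence in the available text assigns the stratum or names these patients in the failure rule. The rest is weaker:
- The blank field is conjecture. CRF page 12 is cited only for the AUC denominator, and the form itself is not in the documents.
- A success needs the fourth case above, and the documents give neither a count nor a success rate for it.
- The word baseline in the stratified test is not plainly an error to be replaced by the infused amount. Protocol 7.1.3 has islet mass counted on the prepared product, so a patient whose islets were isolated but not infused may have a count.

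**Conclusion.** The observation is accurate but calls for no change. It is an unwritten coding detail with an evident answer: no infusion is 0 IEQ/kg, which falls in <2500, and an endpoint defined after a transplant is not met without one. Section 6 of the SAP already tells the analyst that dropping these patients is not allowed.

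The conclusion of the trial does not depend on the stratum choice to any useful degree. At the upper value of 5 patients, average power is 89.9% against 90.2%, the false-positive rate is 2.5% either way, and the decision differs in 1.6% of trials. Larger shifts need lopsided splits; 5:0 and 0:5 each have probability 1/32.

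These figures assume 17/21/12 transplanted patients per arm, the plan's own success rates, and failure for every untransplanted patient. The number actually dosed without a transplant is not given and may be zero. Section 3.2.1 of the addendum could already contain a rule.
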